### **11.1.3 Study primary and secondary endpoints**

#### **11.1.3.1 Primary endpoint/outcome measure**

- 6-month symptom improvement rate using the LCSS ASBI, i.e., proportion of patients who will experience a minimum clinically important improvement in symptoms (*defined as a decrease in the ASBI from enrolment  $\geq$ 10 in two consecutive assessments*) over 6 months of treatment.

Note: A patient will be categorized as having:

- an **improved ASBI** if the mean of any two consecutive post-baseline ASBI assessments for that patient is at least 10 points below the patient's ASBI at enrolment;
- a **worsened ASBI** if the mean of any two consecutive post-baseline ASBI assessments for that patient is at least 10 points above the value at enrolment;
- a **stable ASBI** if the mean of any two consecutive post-baseline ASBI assessments for that patient is within 10 points of the value at enrolment.

[figure not shown]
A change of 10 points on a 0-100 scale is considered sufficient to indicate a clinically meaningful change [32, 33, 34]; this magnitude is about the same as the 0.5 standard deviation that has also reported as a universally acceptable minimum clinically important difference [35].

[figure not shown]

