## **11.6 STUDY SIZE**

Sample size calculation has been based on study's primary endpoint, which involves the determination of the proportion of study population with clinically meaningful improvement in the LCSS ASBI score over a 6-month treatment period.

Due to the lack of published data on the effect of afatinib on symptom burden using the LCSS, the worst case scenario has been taken into account, i.e., that the proportion of patients experiencing symptom improvement (*as defined in Section 11.1.3.1*) after 6 months of therapy will be approximately 0.50. Consequently, the assessment of 96 patients is required to estimate the aforementioned proportion with a margin of error not exceeding 0.10 which represents a scientifically acceptable level of precision of the estimate [95% CI: 0.40-0.60;  $\alpha$ : 0.05; Relative Standard Error (RSE): 10.21%]. This means that for any proportion between 0.05 and 0.95, the precision will range from 0.04 to 0.10 at a 95% confidence limit. The sample size determination has been performed using the statistical software package SAS v9.4 (SAS Institute, Cary, NC).

In order to control for an estimated 25% drop out/non-evaluable rate, 128 patients are finally required in order to ensure the aforementioned sample size for the final statistical analysis.

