## **11.8 DATA ANALYSIS**

The study is not aimed to confirm or reject any pre-defined hypotheses; therefore statistical analyses will be of explorative and descriptive nature.

Continuous variables will be summarized with the use of descriptive statistical measures (mean value, standard deviation, median and extreme values) and categorical/distinct variables will be displayed as frequency tables (N, %). The normality of distribution of continuous variables will be examined using the Shapiro-Wilk test in order to determine whether or not to use parametric methods for the analysis of the sample data.

Differences between the mean values of continuous variables will be evaluated using the paired t-test or the non-parametric analogue (i.e., Wilcoxon signed rank test).

All statistical tests will be two-sided and will be performed at a 0.05 significance level. The exact p-values will be reported, even for non-significant results, rounded to three (3) decimals unless the p-value is less than 0.001 (in such case P<0.001 will be reported). No adjustment for multiplicity of testing will be performed.

A SAP comprising a comprehensive and detailed description of the statistical methodology applied for the purposes of the interim and final analysis along with imputation methods for missing data will be prepared prior to database lock.

Statistical analysis will be conducted using a validated statistical software package [e.g., Statistical Analysis System (SAS)].

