### **11.8.2 Analysis for the primary endpoint**

Pertaining to the primary endpoint the proportion of patients experiencing a minimum clinically important symptom improvement (*as defined in Section 11.1.3.1*) over a 6-month period of treatment will be calculated along with the respective 95% confidence interval; in addition the relevant proportions of patients whose symptom burden has remained stable and deteriorated will be calculated. The 95% confidence interval will be derived from Wald confidence limits for a binomial proportion.

In order to examine the impact of baseline characteristics including among others, gender, age, BMI, educational/marital/employment status, disease stage, histological subtype, sites of metastases, EGFR mutation subtype, smoking status and smoking history, ECOG PS, type of concomitant medications and comorbidities, as well as adherence to therapy at 6 months on the study primary endpoint, a binary logistic regression model will be applied.

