### **11.8.3 Analysis for the secondary endpoints**

With regard to the secondary endpoints pertaining to the LCSS outcome measures, the mean change of the total LCSS, defined as the average value of all individual item scores, will be calculated from enrolment to all available subsequent study visits and will be examined for statistical significance with the use of the paired t-test or its non-parametric analogue. Similar analysis will be performed for the ASBI subscore and each individual domain of LCSS.

If applicable, pertaining to the change of the mean LCSS as well as the mean ASBI through the observation period, linear mixed models will be applied, in order to estimate the monthly predicted change in the aforementioned scores.

Additionally, the symptom improvement rate throughout the study observation period will also be calculated in patient-years.

The distribution of patients by level ('level 1: no problems', 'level 2: some problems' and 'level 3: extreme problems') for each dimension (mobility, self-care, usual activities, pain/discomfort, anxiety/ depression) as well as the distribution of patients in the dichotomized EQ-5D levels ['no problems' (level 1) and 'problems' (levels 2 and 3)] will be presented in frequency tables (N, %) for all patients with available data. Descriptive statistical measures will be calculated for the EQ-VAS score at each predefined study time-point.

The McNemar's test will be used in order to evaluate the change in the levels ('with problems'/ 'no problems') of each dimension between enrolment and the post-baseline visits.

Descriptive statistics of the EQ-VAS will be presented for each study visit as well as for the observed changes in the EQ-VAS from the enrolment visit to each post-baseline study time-point; while the paired t-test or the Wilcoxon signed rank test will be used to assess the statistical significance of the change.

The distribution of patients in the different ECOG performance status levels at every study time-point will be presented in frequency tables (N, %). Additionally, changes in the status of patients from baseline to post-baseline evaluations will be depicted in shift tables.

Adherence to treatment with afatinib as well as the proportions of patients who discontinued or interrupted treatment, and those who underwent any dose modifications along with the type of dosage modifications and reasons for these, will be analysed in a descriptive manner.

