## 3 DATA ANALYSIS CONSIDERATIONS

### 3.1 General presentation of summaries and analyses

Statistical analysis and generation of tables and patient data listings will be performed using SAS® statistical analysis software (the most updated version at the time of analysis onset). Figures will be created by validated graph programs, such as SAS® and/or Microsoft Excel.

Summary statistics will consist of frequency tables ( $n_{pt}$ , %) for categorical variables. For continuous variables, descriptive statistics [number of patients with available observations ( $n_{pt}$ ), number of missing observations ( $n_{miss}$ ), mean, standard deviation (SD), median, 25th and 75th percentiles, minimum (min) and maximum (max)] will be tabulated.

The normality of distribution of continuous variables will be examined using the Shapiro-Wilk test. Concerning binomial proportions 95% CIs will be derived from Wald confidence limits for binomial proportions. In order to examine the differences in the values of continuous variables, the paired t-test or the Wilcoxon signed-rank test for two dependent samples will be used. The association between categorical variables will be assessed with the use of the McNemar's test for paired samples.

Potentially, linear mixed-effects models for repeated-measures will be fitted in order to describe the trend of continuous variables over time. The impact of patient characteristics on variables of interest will be evaluated with the use of logistic regression models for dichotomous outcome variables. Pertaining to data presentation, when reporting relative frequencies or other percent values the following rules will apply:

- ✓ For values where all patients fulfil a certain criterion, the percent value will be displayed as 100.0.

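### In the readable text, patient characteristics are related to symptom change only through a yes/no cut of the ASBI; a linear mixed model alongside the logistic one would use the same data more efficiently

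*Protocol*

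**What the plan says.** The ASBI is the mean of six items, each marked on a 100-mm scale (Protocol 11.5, SAP 3.7.2). It is collected at enrolment and at months 2, 4 and 6 for the primary objective. Protocol 11.1.3.1 calls a patient improved when the mean of two consecutive post-baseline ASBI values lies at least 10 points below enrolment. It adds that "this magnitude is about the same as the 0.5 standard deviation".

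For the role of patient characteristics, Protocol 11.8.2 lists the candidates and continues "as well as adherence to therapy at 6 months on the study primary endpoint, a binary logistic regression model will be applied". SAP 3.1 states: "The impact of patient characteristics on variables of interest will be evaluated with the use of logistic regression models for dichotomous outcome variables". SAP 4.1 lists the covariates without naming a further model. The protocol abstract describes the same analysis more loosely, as generalized linear models on the primary endpoint.

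On its continuous scale, the ASBI is analysed by paired tests. Protocol 11.8.3 adds that, if applicable, "linear mixed models will be applied, in order to estimate the monthly predicted change in the aforementioned scores". No patient characteristic is named there or in the matching sentence of SAP 3.1. Protocol 11.10 allows for multivariable analyses if they are thought necessary, but specifies none. SAP section 8, to which SAP 4.2 and 7 refer, is not readable in the public copy.

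**The concern.** Protocol 11.4.4 puts the covariate question in terms of change in symptom burden, which is a matter of degree. The model that can be read answers it with a yes/no outcome. A fall of 9 points and a rise of 20 then count the same, as do falls of 11 and of 40. Stable and worsened patients are merged, although Protocol 11.8.2 reports them separately in the description.

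At stake is the search for associated factors. Each test is judged at the 0.05 level in about 96 patients, so associations that the collected scores could show may be missed. The two-consecutive rule also leaves a patient with a single post-baseline ASBI without a logistic outcome, whereas a mixed model can use that value.

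**Working it through.** **Plan inputs.** "All statistical tests will be two-sided and will be performed at a 0.05 significance level" (Protocol 11.8). Protocol 11.6 gives the sample size, "the assessment of 96 patients is required to estimate the aforementioned proportion with a margin of error not exceeding 0.10", with an improvement rate that "after 6 months of therapy will be approximately 0.50". It adds: "In order to control for an estimated 25% drop out/non-evaluable rate, 128 patients are finally required". The SD is not stated. If 10 points is 0.5 SD, then SD = 10/0.5 = 20.

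**Assumed, because the documents give no figure.** One binary characteristic, its split, its effect on post-baseline ASBI, the correlation ρ between visits, and normal scores.

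**Step 1, the plan's own figure.** n = 1.96² × 0.5 × 0.5 / 0.10² = 96.04, against 96 in the plan. At 96 the half-width is 1.96 × √(0.25/96) = 0.100 and the relative standard error is √(0.25/96)/0.5 = 10.21%. Then 96/(1 − 0.25) = 128. All reproduce.

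**Step 2, simple comparison.** Take 48 versus 48 patients, a 10-point effect, and SD 20 for the analysed change.
- Linear: SE = 20 × √(2/48) = 4.08; 10/4.08 = 2.449; power = Φ(2.449 − 1.960) = 0.688.
- Cut so that 50% improve: the group rates are Φ(−0.25) = 0.40 and Φ(0.25) = 0.60, and the power of the two-proportion test is 0.490.
- Loss: 19.8 points. A median cut of a normal score keeps about 2/π = 64% of the information.

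**Step 3, the plan's actual rule.** Four visits are simulated with SD 20 at each visit and equal correlation ρ. A patient is improved if the mean of months 2 and 4, or of months 4 and 6, is at least 10 below enrolment. The overall rate is set to 50%. The logistic likelihood-ratio test is compared with a linear model of (mean of months 2, 4 and 6) minus enrolment. Neither model includes enrolment ASBI as a covariate. There are 1000 replicates, so the Monte Carlo standard error is at most √(0.25/1000) = 0.016.

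The linear side can be checked by hand. Variance = 400 × [(1 + 2ρ)/3 + 1 − 2ρ]. At ρ = 0.5 this is 266.7, so SD = 16.33 and SE = 16.33 × √(2/48) = 3.33. Then 10/3.33 = 3.00 and Φ(3.00 − 1.96) = 0.85.

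| Shift (points), 50:50 split | ρ | Logistic | Linear | Gain (points) |
|---|---|---|---|---|
| 10 | 0.3 | 0.51 | 0.73 | 22 |
| 10 | 0.5 | 0.64 | 0.85 | 21 |
| 10 | 0.7 | 0.85 | 0.97 | 12 |
| 7.5 | 0.5 | 0.40 | 0.58 | 18 |
| 7.5 | 0.7 | 0.63 | 0.82 | 19 |
| 5 | 0.5 | 0.22 | 0.32 | 10 |

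Over shifts of 5 to 10 points, splits of 50:50 and 30:70, and ρ from 0.3 to 0.7, the gain is about 6 to 22 points. The low end comes from the 5-point shifts.

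**Step 4, checks.**
- With no effect (ρ = 0.5), rejection is 0.052 for logistic and 0.053 for linear, so the gain does not come from a liberal test.
- With enrolment ASBI in both models (10 points, 50:50, ρ = 0.5), power is 0.750 against 0.963.
- Smaller effects: for 4 points the closed form of step 2 gives 16.4% against 11.8% (50:50) and 12.0% against 8.9% (20:80), a gain of about 3 to 5 points.
- Lower improvement rates: in the closed form the loss reaches about 25 points at a rate of 0.30 and about 33 at 0.20.

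**The case against.** The strongest reply is that Protocol 11.8.2 asks about the primary endpoint, that endpoint is binary, and logistic regression is the matching model. This stands. A reader might infer that the logistic model is a mistake, or that a linear model should replace it. The documents support neither. Which patients reach a clinically important improvement is a legitimate question, and a linear model answers a different one.

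Second, SAP section 8 cannot be read, and SAP 3.1 is a general paragraph that does not confine covariates to logistic models. This also stands. It would be too strong to say that the plan has no covariate model of the ASBI score; the point covers only the text that can be read.

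Third, the study is declared exploratory and was sized for the precision of one proportion. No power target is missed, and the figures do not show an underpowered study. They compare two ways of using the same data. Even an exploratory search that reports p-values at 0.05 benefits from the more efficient one.

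Fourth, the 10-point threshold is a change within a patient. A reader might take the 10-point row as a difference between groups that the plan calls meaningful; the plan says no such thing. The shifts are illustrations. At 5 points both models usually miss the effect, and at 10 points with ρ = 0.7 the logistic model already has 0.85 power.

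Fifth, the figures test one characteristic at a time, while Protocol 11.4.4 lists more than a dozen. They do not describe the full multivariable model, where about 0.5 × 96 = 48 responders would be spread thinly.

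Last, SAP 4.2 partly covers patients with few assessments. If more than 20% are non-evaluable, the primary analysis is repeated in those with at least one post-baseline ASBI. Whether this extends to the covariate model is not visible.

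**Conclusion.** The point holds as an inexpensive improvement, not as a correction of an error. In the readable text, the link between patient characteristics and symptom burden is examined only through the improved/not-improved cut. The planned mixed model of the score itself names no characteristics.

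The size of about 6 to 22 percentage points of power is conditional on the plan's 96 patients and 50% rate, the implied SD of about 20, one binary characteristic shifting ASBI by 5 to 10 points, and the assumed visit correlations. The linear model was ahead in every scenario with an effect, but the amount depends on inputs that the plan does not give. The primary proportion and its confidence interval are unaffected.

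**What to change.** Keep the responder proportion with its 95% CI and the binary logistic model as planned. Alongside it, in Protocol 11.8.2 and SAP 3.1 (and SAP section 8 if it does not already do so), add a linear mixed model of ASBI at months 2, 4 and 6. Use enrolment ASBI and the listed characteristics as covariates, and report each effect in ASBI points with a 95% CI. The model can include patients with an enrolment ASBI and only one post-baseline ASBI.

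No new data are needed. The cost is SAP wording and one more exploratory model with p-values unadjusted for multiplicity. The model also assumes roughly linear effects on a score bounded at 0 and 100, which should be checked from the residuals.

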## 4 STATISTICAL/ANALYTICAL ISSUES

### 4.1 Adjustments for covariates

The following variables will be considered as potential confounders or effect modifiers of the impact of treatment with afatinib on the improvement in disease-specific symptom burden.

- ✓ Age at baseline;
- ✓ Gender;
- ✓ BMI at baseline;
- ✓ Educational/marital/employment status;
- ✓ Baseline comorbidity count with particular emphasis on gastrointestinal, psychiatric, and musculoskeletal and connective tissue disorders;

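### If the 16 characteristics in protocol 11.8.2 enter one unpenalised logistic model, about 48 expected events must support some 27 to 46 coefficients, and its odds ratios and p-values would be unreliable

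*Protocol*

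**What the plan says.** Protocol 11.8.2 sets out the primary proportion with a Wald interval. It then says that, to examine the impact of patient characteristics on the primary endpoint, "a binary logistic regression model will be applied". It names 16 characteristics, and the list is open-ended: gender, age, BMI, education, marital status, employment, stage, histology, metastatic sites, EGFR subtype, smoking status, smoking history, ECOG PS, concomitant medications, comorbidities and 6-month adherence.

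SAP 4.1 repeats a similar list as potential confounders or effect modifiers. Some entries have no fixed coding, for example "Baseline comorbidity count with particular emphasis on gastrointestinal, psychiatric, and musculoskeletal and connective tissue disorders".

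On size, protocol 11.6 assumes that the proportion improving "after 6 months of therapy will be approximately 0.50" and states that "the assessment of 96 patients is required to estimate the aforementioned proportion with a margin of error not exceeding 0.10". On testing, protocol 11.8 says "All statistical tests will be two-sided and will be performed at a 0.05 significance level" and "No adjustment for multiplicity of testing will be performed".

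The model wording is not uniform. Section 11.8.2 uses the singular. The protocol abstract (generalized linear models) and SAP 3.1 (logistic regression models) use the plural. Protocol 11.10 makes multivariable adjustment for confounding conditional on its being judged necessary.

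**The concern.** The sample size was chosen for the precision of one proportion, not for a regression. What a logistic model can support depends mainly on the smaller outcome group, here at most about 48 patients, and on the number of coefficients rather than the number of named factors. Several factors have three to five categories, so 16 names become many more coefficients.

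With so few events per coefficient, unpenalised maximum likelihood pushes odds ratios away from 1, and Wald tests reject too often. Exact p-values are to be reported at 0.05 without multiplicity adjustment, so spurious or exaggerated predictors of symptom improvement could reach the study report with nothing to flag them. In the visible text, no coding, variable-selection rule or shrinkage limits the number of coefficients.

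**Working it through.** **1. The plan's own figure.** With p = 0.50 and half-width 0.10, n = 1.96² × 0.50 × 0.50 / 0.10² = 96.04, which rounds to the stated 96. Relative standard error = √(0.25/96)/0.50 = 10.21%, as stated. Enrolment = 96/(1 − 0.25) = 128, as stated. The sample-size figures reproduce.

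**2. Events.** 96 × 0.50 = 48 improved and 48 not improved. The value 0.50 is the worst case for precision but the best case here, because any other rate shrinks the smaller group. As an illustration, a 30% rate gives 96 × 0.30 ≈ 29 events.

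**3. Coefficients.** A factor with L categories needs L − 1. Levels are from protocol 11.4.3; age, BMI and pack-years are taken as linear.

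| Factor | Coefficients |
|---|---|
| Age, gender, BMI | 1 + 1 + 1 |
| Education (4 levels) | 3 |
| Marital status (4) | 3 |
| Employment (5) | 4 |
| Stage (IIIB, IV) | 1 |
| Histology (3) | 2 |
| EGFR subtype (3) | 2 |
| Smoking status (4) | 3 |
| Pack-years | 1 |
| **Subtotal** | **22** |

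The other five factors need assumptions about coding:

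| Factor | Low | Middle | High |
|---|---|---|---|
| ECOG PS | 1 | 2 | 4 |
| Metastatic sites | 1 | 1 | 5 |
| Comorbidities | 1 | 1 | 4 |
| Concomitant medications | 1 | 5 | 10 |
| Adherence | 1 | 1 | 1 |
| **Added** | **5** | **10** | **24** |
| **Total with the 22** | **27** | **32** | **46** |

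The middle value for medications uses the five drug classes named in protocol 11.4.4. The high value allows each class at two time points.

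**4. Events per coefficient.**
- 27 coefficients: 48/27 = 1.78
- 32 coefficients: 48/32 = 1.50
- 46 coefficients: 48/46 = 1.04
- One coefficient for each of the 16 factors: 48/16 = 3.0
- All 128 enrolled patients evaluable (64 events), 32 coefficients: 64/32 = 2.0

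**5. Consequence, by simulation.** The setting was n = 96, about 50% events, independent covariates (five standard normal, the rest binary), one true odds ratio of 2 per SD and all other effects null, fitted by unpenalised maximum likelihood.

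| Coefficients | Median estimate of a true OR of 2 | False positives per null coefficient (nominal 5%) |
|---|---|---|
| 32 | about 3.5 | about 11% |
| 27 | about 2.9 | about 10% |
| 16 | about 2.3 | about 7% |
| 6 | about 2.1 | about 5% |

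Repeat runs agreed to within about 0.1 in the odds ratio and one percentage point in the error rate. With all 128 patients evaluable and 32 coefficients, the median was 2.74 and the error rate 9.1%.

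With 32 coefficients at n = 96, at least one null factor was significant in 94% of runs. Much of that is plain multiplicity: 31 independent tests at a true 5% would give 1 − 0.95³¹ = 80%. The cleaner signs of overfitting are the inflated odds ratio, the error rate per coefficient, and an out-of-sample calibration slope of 0.08 (0.28 with 16 coefficients), where 1 is ideal.

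**The case against.** The strongest reply is that the deciding text cannot be seen. SAP 4.2 and SAP 7 refer to Sections 8.1.3 and 8.2, so an efficacy section exists, but its text is not available. Coding, screening or separate models could be specified there and must not be treated as absent. The plural wording in the abstract and SAP 3.1, the word potential in SAP 4.1 and the conditional wording of protocol 11.10 all leave room for something smaller than one full model. The study is also declared explorative and descriptive.

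This stands as far as it goes: the documents do not fix one model of 32 coefficients, and a reader who takes that figure as planned goes too far. It does not remove the point. Section 11.8.2, read as written, describes a single model, and the result does not hinge on 32, since 16 coefficients already leave 3.0 events each. An exploratory label explains the lack of a hypothesis; it does not make inflated odds ratios informative.

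Two other inferences should be resisted:

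- A reader might take the Akaike Information Criterion in the SAP abbreviations as a sign of stepwise selection. It appears nowhere else in the visible text and may equally belong to the linear mixed models.
- A reader might see this model as the plan's only means of separating the drug's effect from comorbidity and co-medication. Protocol 11.10 speaks of multivariable analyses in general. With no control group, which that section acknowledges, regressing response on patient characteristics could not isolate a drug effect at any sample size. The stated aim in 11.8.2 is only to examine the influence of characteristics on the endpoint.

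**Conclusion.** The point holds in conditional form. If the factors in protocol 11.8.2 enter one unpenalised logistic model, there are about 1.0 to 1.8 events per coefficient (3.0 at the most economical coding), and odds ratios and p-values would be materially distorted.

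This rests on 96 evaluable patients, a 0.50 improvement rate, the levels in 11.4.3 and the assumed coding of five factors. The simulated sizes also assume independent covariates and a single true effect, so they are indicative rather than predictions for this data set.

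The reach is limited to a supporting exploratory analysis. The primary proportion and its Wald interval do not depend on this model.

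**What to change.** In protocol 11.8.2, and in the matching SAP text, replace the unpenalised full-list model with one of the following:

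- a penalised logistic model (Firth or ridge) on the full list, with the coding of every factor stated; or
- a short list of about 5 to 6 coefficients, fixed before database lock, with the remaining factors reported as unadjusted descriptive comparisons. At 48 events this gives 48/6 = 8 to 48/5 = 9.6 events per coefficient.

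Reconcile the singular wording in 11.8.2 with the plural in the protocol abstract and SAP 3.1, and confirm that SAP Section 8 says the same.

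The cost is wording only, with no new data or patients. The downside is that estimates are shrunken under the first option, and fewer factors are adjusted jointly under the second.
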